6.8. Concomitant Therapy

Use of prescription or nonprescription drugs and dietary and herbal supplements are prohibited within 7 days or 5 half-lives (whichever is longer) prior to the first dose of study intervention. Limited use of nonprescription medications that are not believed to affect participant safety or the overall results of the study may be permitted on a case-by-case basis following approval by the sponsor. Acetaminophen/paracetamol may be used at doses of ≤ 1 g/day.

Hormonal contraceptives that meet the requirements of this study are allowed to be used in participants who are WOCBP (see [Appendix 4](#)).

For participants with ***renal impairment***, stable concomitant medications (including herbal supplements) may be given following **approval by the sponsor** if they are considered necessary for the welfare of the study participants (eg, standard therapy for underlying diseases), are not contraindicated with the IP (see [Appendix 8](#)), and are unlikely to interfere with the PK of the IP.

As PF-07321332 and ritonavir are both primarily metabolized by CYP3A4, concomitant use of any medications or substances that are strong inducers of CYP3A4 are prohibited within 28 days prior to dosing of investigational product. Additionally, ritonavir and PF-07321332 are inhibitors of CYP3A4. Therefore, medications highly dependent on CYP3A4 for clearance and for which elevated plasma concentrations may be associated with serious and/or life-threatening events are not permitted during dosing of PF-07321332/ritonavir. A non-exhaustive list of prohibited and precautionary medications is provided in [Appendix 8](#). If a medication is not listed, it should not automatically be assumed it is safe to co-administer.

All concomitant treatments taken during the study must be recorded with indication, daily dose, and start and stop dates of administration. All participants will be questioned about concomitant treatment at each clinic visit.

Treatments taken within 28 days before the first dose of study intervention will be documented as a prior treatment. Treatments taken after the first dose of study intervention will be documented as concomitant treatments.

6.8.1. Participants with Healthy Renal Function (Cohort 3 Only)

In general, participants will abstain from all concomitant treatments (prescription or over the counter) as described in Protocol [Section 6.8](#), except for the treatment of AEs. Of note, the following **restrictions** apply:

- Limited use of nonprescription medications that are not believed to affect participant safety or the overall results of the study may be permitted on a case-by-case basis ***after*** approval by the sponsor.

6.8.2. Participants with Impaired Renal Function (Cohort 1, and Cohorts 2 & 4 [If Applicable])

Participants are permitted to be on stable doses of background medications if they are considered necessary for the welfare of the study participants (eg, standard therapy for the underlying disease), are not contraindicated with the investigational product, and are unlikely to interfere with the PK of the investigational product. ***Whenever possible***, attempts must be made to **not** alter the doses and regimens of the concomitant medications after Day 1 and until the end of study on Day 3.

- Approved concomitant medications should be administered to renally impaired participants at least 2 hours prior to dosing or withheld until 4 hours after PF-07321332 dosing.

6.8.3. Rescue Medicine

There is no rescue therapy to reverse the AEs observed with PF-07321332 or ritonavir; standard medical supportive care must be provided to manage the AEs.

7. DISCONTINUATION OF STUDY INTERVENTION AND PARTICIPANT DISCONTINUATION/WITHDRAWAL

7.1. Discontinuation of Study Intervention

It may be necessary for a participant to permanently discontinue study intervention. Reasons for permanent discontinuation of study intervention include the following

- AE requiring discontinuation in investigator's view;
- Pregnancy;
- Positive COVID-19 test.

Note that discontinuation of study intervention does not represent withdrawal from the study. If study intervention is permanently discontinued, the participant will remain in the study to be evaluated for safety and PK, if possible. See the [SoA](#) for data to be collected at the time of discontinuation of study intervention and follow-up for any further evaluations that need to be completed.

In the event of discontinuation of study intervention, it must be documented on the appropriate CRF/in the medical records whether the participant is discontinuing further receipt of study intervention or also from study procedures, posttreatment study follow-up, and/or future collection of additional information.

7.2. Participant Discontinuation/Withdrawal From the Study

A participant may withdraw from the study at any time at his/her own request. Reasons for discontinuation from the study include the following:

- Refused further study procedures;
- Lost to follow-up;
- Death;
- Study terminated by sponsor;

At the time of discontinuing from the study, if possible, an early discontinuation visit should be conducted. See the [SoA](#) for assessments to be collected at the time of study discontinuation and follow-up and for any further evaluations that need to be completed.

The early discontinuation visit applies only to participants who are enrolled/randomized and then are prematurely withdrawn from the study. Participants should be questioned regarding their reason for withdrawal.

If a participant withdraws from the study, he/she may request destruction of any remaining samples taken and not tested, and the investigator must document any such requests in the site study records and notify the sponsor accordingly.

If the participant withdraws from the study and also withdraws consent (see Section 7.2.1) for disclosure of future information, no further evaluations should be performed and no additional data should be collected. The sponsor may retain and continue to use any data collected before such withdrawal of consent.

7.2.1. Withdrawal of Consent

Participants who request to discontinue receipt of study intervention will remain in the study and must continue to be followed for protocol-specified follow-up procedures. The only exception to this is when a participant specifically withdraws consent for any further contact with him or her or persons previously authorized by the participant to provide this information. Participants should notify the investigator in writing of the decision to withdraw consent from future follow-up, whenever possible. The withdrawal of consent should be explained in detail in the medical records by the investigator, as to whether the withdrawal is only from further receipt of study intervention or also from study procedures and/or posttreatment study follow-up, and entered on the appropriate CRF page. In the event that vital status (whether the participant is alive or dead) is being measured, publicly available

information should be used to determine vital status only as appropriately directed in accordance with local law.

7.3. Lost to Follow-Up

A participant will be considered lost to follow-up if he or she repeatedly fails to return for scheduled visits and is unable to be contacted by the study site.

The following actions must be taken if a participant fails to return to the clinic for a required study visit:

- The site must attempt to contact the participant and reschedule the missed visit as soon as possible. Counsel the participant on the importance of maintaining the assigned visit schedule and ascertain whether the participant wishes to and/or should continue in the study;
- Before a participant is deemed lost to follow-up, the investigator or designee must make every effort to regain contact with the participant (where possible, 3 telephone calls and, if necessary, a certified letter to the participant's last known mailing address or local equivalent methods). These contact attempts should be documented in the participant's medical record;
- Should the participant continue to be unreachable, he/she will be considered to have withdrawn from the study.

8. STUDY ASSESSMENTS AND PROCEDURES

The investigator (or an appropriate delegate at the investigator site) must obtain a signed and dated ICD before performing any study-specific procedures.

Study procedures and their timing are summarized in the [SoA](#). Protocol waivers or exemptions are not allowed.

Safety issues should be discussed with the sponsor immediately upon occurrence or awareness to determine whether the participant should continue or discontinue study intervention.

Adherence to the study design requirements, including those specified in the [SoA](#), is essential and required for study conduct.

All screening evaluations must be completed and reviewed to confirm that potential participants meet all eligibility criteria. The investigator will maintain a screening log to record details of all participants screened and to confirm eligibility or record reasons for screening failure, as applicable.

Participants will be screened within 28 days prior to administration of the study intervention to confirm that they meet the study population criteria for the study. If the time between

screening and dosing exceeds 28 days as a result of unexpected delays (eg, delayed drug shipment), then participants do not require rescreening if the laboratory results obtained prior to first dose administration meet eligibility criteria.

A participant who qualified for this protocol but did not enroll from an earlier cohort/group may be used in a subsequent cohort/group without rescreening, provided laboratory results obtained prior to the first dose administration meet eligibility criteria for this study. In addition, other clinical assessments or specimen collections, eg, banked biospecimens, may be used without repeat collection, as appropriate.

Every effort should be made to ensure that protocol-required tests and procedures are completed as described. However, it is anticipated that from time to time there may be circumstances outside the control of the investigator that may make it unfeasible to perform the test. In these cases, the investigator must take all steps necessary to ensure the safety and well-being of the participant. When a protocol-required test cannot be performed, the investigator will document the reason for the missed test and any corrective and preventive actions that he or she has taken to ensure that required processes are adhered to as soon as possible. The study team must be informed of these incidents in a timely manner.

If an IV catheter is utilized for blood sample collections, ECGs and vital sign assessments (pulse rate and BP) should be collected prior to the insertion of the catheter.

For samples being collected and shipped, detailed collection, processing, storage, and shipment instructions and contact information will be provided to the investigator site prior to initiation of the study.

The total blood sampling volume for individual participants in this study is approximately 105 mL. The actual collection times of blood sampling may change. Additional blood samples may be taken for safety assessments at times specified by Pfizer, provided the total volume taken during the study does not exceed 550 mL during any period of 60 consecutive days.

To prepare for study participation, participants will be instructed on the information in Protocol [Section 5.3](#) Lifestyle Considerations and [Section 6.8](#) Concomitant Therapy.

8.1. Efficacy Assessments

Not applicable.

8.2. Safety Assessments

Planned time points for all safety assessments are provided in the [SoA](#). Unscheduled clinical laboratory measurements may be obtained at any time during the study to assess any perceived safety issues.

8.2.1. Physical Examinations

A complete physical examination will include, at a minimum, head, ears, eyes, nose, mouth, skin, heart and lung examinations, lymph nodes, and gastrointestinal, musculoskeletal, and neurological systems.

A brief physical examination will include, at a minimum, assessments of general appearance, the respiratory and cardiovascular systems, and participant-reported symptoms.

Physical examinations may be conducted by a physician, trained physician's assistant, or nurse practitioner as acceptable according to local regulation.

Height and weight will also be measured and recorded as per the [SoA](#). For measuring weight, a scale with appropriate range and resolution is used and must be placed on a stable, flat surface. Participants must remove shoes, bulky layers of clothing, and jackets so that only light clothing remains. They must also remove the contents of their pockets and remain still during measurement of weight.

Physical examination findings collected during the study will be considered source data and will not be required to be reported, unless otherwise noted. Any untoward physical examination findings that are identified during the active collection period and meet the definition of an AE or SAE ([Appendix 3](#)) must be reported according to the processes in [Sections 8.3.1 to Section 8.3.3](#).

8.2.2. Vital Signs

Supine BP will be measured with the participant's arm supported at the level of the heart, and recorded to the nearest mm Hg after approximately 5 minutes of rest. The same arm (preferably the dominant arm) will be used throughout the study. Participants should be instructed not to speak during measurements.

The same properly sized and calibrated BP cuff will be used to measure BP each time. The use of an automated device for measuring BP and pulse rate is acceptable; however, when done manually, pulse rate will be measured in the brachial/radial artery for at least 30 seconds. When the timing of these measurements coincides with a blood collection, BP and pulse rate should be obtained prior to the nominal time of the blood collection.

Additional collection times, or changes to collection times, of BP and pulse rate will be permitted, as necessary, to ensure appropriate collection of safety data.

8.2.2.1. Respiratory Rate

Respiratory rate will be measured after approximately 5 minutes of rest in a supine position by observing and counting the respirations of the participant for 30 seconds and multiplying by 2. When BP is to be taken at the same time, respiration measurement will be done during the 5 minutes of rest and before BP measurement.

8.2.2.2. Temperature

Temperature will be measured orally other body locations, eg tympanic, are acceptable provided the same method is used and documented throughout the study). No eating, drinking, or smoking is allowed for 15 minutes prior to the measurement.

8.2.3. Electrocardiograms

Standard 12-lead ECGs utilizing limb leads (with a 10 second rhythm strip) should be collected at times specified in the **SoA** section of this protocol using an ECG machine that automatically calculates the heart rate and measures PR, QT, and QTc intervals and QRS complex. Alternative lead placement methodology using torso leads (eg, Mason-Likar) should not be used given the potential risk of discrepancies with ECGs acquired using standard limb lead placement. All scheduled ECGs should be performed after the participant has rested quietly for at least 5 minutes in a supine position.

To ensure safety of the participants, a qualified individual at the investigator site will make comparisons to baseline measurements. Additional ECG monitoring will occur if a) a postdose QTcF interval is increased by ≥ 30 msec from the baseline and is > 450 msec for participants with normal renal function and > 470 msec for participants with impaired renal function; or b) an absolute QT value is ≥ 500 msec for any scheduled ECG. If either of these conditions occurs, then 2 additional ECGs will be collected approximately 2 to 4 minutes apart to confirm the original measurement. If the QTc values from these repeated ECGs remain above the threshold value, then a single ECG must be repeated at least hourly until QTc values from 2 successive ECGs fall below the threshold value that triggered the repeat measurement.

If a) a postdose QTcF interval remains ≥ 30 msec from the baseline **and** is > 450 msec for participants with normal renal function and > 470 msec for participants with impaired renal function; or b) an absolute QT value is ≥ 500 msec for any scheduled ECG for greater than 4 hours (or sooner, at the discretion of the investigator); or c) QTcF intervals get progressively longer, the participant should undergo continuous ECG monitoring. A cardiologist should be consulted if QTcF intervals do not return to less than the criteria listed above after 8 hours of monitoring (or sooner, at the discretion of the investigator).

In some cases, it may be appropriate to repeat abnormal ECGs to rule out improper lead placement as contributing to the ECG abnormality. It is important that leads be placed in the same positions each time in order to achieve precise ECG recordings. If a machine-read QTc value is prolonged, as defined above, repeat measurements may not be necessary if a qualified medical provider's interpretation determines that the QTcF values are in the acceptable range.

ECG values of potential clinical concern are listed in [Appendix 7](#).

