10. Previous administration with an investigational drug within 30 days (or as determined by the local requirement) or 5 half-lives preceding the first dose of study intervention used in this study (whichever is longer).

Diagnostic Assessments:

11. A positive urine drug test, for illicit drugs, at Screening:

NOTE: repeat urine drug testing is **not** permitted in this study.

Renal impairment participants may be eligible to participate after approval from sponsor if their drug screen is positive for a prescribed substance that is not expected to interfere with the PK of PF-07321332.

12. Baseline standard 12-lead ECG that demonstrates:

- Clinically relevant abnormalities requiring treatment (eg, acute myocardial infarction, serious tachy- or brady-arrhythmias) or indicating serious underlying heart disease (eg, prolonged PR interval, cardiomyopathy, underlying structural heart disease, Wolff Parkinson-White syndrome);
- Confirmed QTcF >450 msec for participants with normal renal function and >470 msec for participants with impaired renal function

13. Participants with **ANY** of the following abnormalities in clinical laboratory tests at screening, as assessed by the study-specific laboratory and confirmed by a single repeat test, if deemed necessary:

- AST **or** ALT level $>2 \times$ ULN;
- Total bilirubin level $\geq 1.5 \times$ ULN; participants with a history of Gilbert's syndrome may have direct bilirubin measured and would be eligible for this study provided the direct bilirubin level is \leq ULN.

14. In the opinion of the investigator or Pfizer (or designee), have any clinically significant laboratory abnormality that could affect interpretation of study data or the participant's participation in the study.

15. Screening laboratory tests with abnormal results may be repeated **once** to confirm abnormal results (with the same screening number); the last value will be used to determine eligibility.

16. Sites may be permitted to re-screen participants (with a new screening number) who initially do not meet eligibility criteria **once** following agreement with the sponsor.

Other Exclusions:

17. History of regular alcohol consumption exceeding 7 drinks/week for females or 14 drinks/week for males (1 drink = 5 ounces [150 mL] of wine or 12 ounces [360 mL] of beer or 1.5 ounces [45 mL] of hard liquor) or binge drinking and/or any

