EU	European Union
EudraCT	European Clinical Trials Database
FDA	Food and Drug Administration
FIH	first-in-human
f _m	fraction metabolized
FSH	follicle stimulating hormone
f _u	fraction unbound
GCP	Good Clinical Practice
GGT	gamma-glutamyl transferase
GFR	glomerular filtration rate

Abbreviation	Term
GLP	Good Laboratory Practice
h	hour
HBcAb	hepatitis B core antibody
HBsAg	hepatitis B surface antigen
HCoV-OC43	human coronavirus OC43
HCoV-229E	human coronavirus 229E
HCoV-HKU1	human coronavirus HKU1
HCoV-NL63	human coronavirus NL63
HCVAb	hepatitis C antibody
HCV	hepatitis C virus
hep C	hepatitis C
HIV	human immunodeficiency virus
HMG CoA reductase	3-hydroxy-3-methyl-glutaryl-CoA reductase
HR	heart rate
HRT	hormone replacement therapy
IB	Investigator's Brochure
ICD	informed consent document
ICH	International Council for Harmonisation
ID	identification
IMP	investigational medicinal product
IND	Investigational New Drug
INR	international normalized ratio
IP	investigational product
IP manual	investigational product manual
IPAL	Investigational Product Accountability Log
IRB	Institutional Review Board
ISO	International Organization for Standardization
IV	intravenous
KDOQI	Kidney Disease Outcomes Quality Initiative
k_{el}	terminal phase rate constant calculated by a linear regression of the log-linear concentration-time curve.
K_i	inhibition constant
LFT	liver function test
MAD	multiple ascending dose
MCH	mean corpuscular hemoglobin
MCHC	mean corpuscular hemoglobin concentration
MCV	mean corpuscular volume
MERS	Middle East respiratory syndrome
msec	millisecond
mg	milligram
mL	milliliter
N/A	not applicable

Abbreviation	Term
NHP	non-human primate
NNRT	non-nucleoside reverse transcriptase
NOAEL	no observed adverse effect level
PACL	Protocol Administrative Change Letter
PAH	pulmonary arterial hypertension
PCR	polymerase chain reaction
PD	pharmacodynamic(s)
PDE-5	phosphodiesterase type 5
pH	potential of hydrogen
PK	pharmacokinetic(s)
PT	prothrombin time
PT-INR	prothrombin time-international normalized ratio
PVC	premature ventricular contraction/complex
q12h	every 12 hours
QT	time from the beginning of the QRS complex to the end of the T wave
QTc	corrected QT interval
QTcF	corrected QT (Fridericia method)
qual	qualitative
RBC	red blood cell
RNA	ribonucleic acid
RT-PCR	reverse-transcriptase polymerase chain reaction
S1	Screening Visit 1
S2	Screening Visit 2
SAD	single ascending dose
SAE	serious adverse event
SAP	Statistical Analysis Plan

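### The QT ≥500 msec trigger in Protocol Section 8.2.3 is confirmed and released on QTc, so at slow heart rates the hourly repeat ECGs need not start

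*Protocol*

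**What the plan says.** The rule in Protocol Section 8.2.3 has four steps.

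- **Trigger.** Either (a) a postdose QTcF that is up by 30 msec or more and above 450 msec (normal renal function) or 470 msec (impaired), or (b) "an absolute QT value is ≥ 500 msec for any scheduled ECG".
- **Confirmation and start.** Two further ECGs are taken a few minutes apart to confirm the finding. "If the QTc values from these repeated ECGs remain above the threshold value", single ECGs become mandatory at least hourly.
- **Stop.** The hourly ECGs run "until QTc values from 2 successive ECGs fall below the threshold value that triggered the repeat measurement".
- **Escalation.** Continuous monitoring follows if the QTcF condition persists, if QT stays at or above 500 msec for more than 4 hours (or sooner at the investigator's discretion), or if QTcF lengthens progressively. Then: "A cardiologist should be consulted if QTcF intervals do not return to less than the criteria listed above after 8 hours of monitoring".

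The start and stop sentence names no correction. Appendix 9 defines QTc only as "corrected QT interval" and lists QTcF, the Fridericia version, separately. The baseline exclusion in Section 5.2.1 (criterion 12) is on the Fridericia scale: "Confirmed QTcF >450 msec for participants with normal renal function and >470 msec for participants with impaired renal function". The Schedule of Activities has single ECGs at Screening, Day 1 and Day 3.

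**The concern.** A trigger and its release should be on the same measure. Under (b) the trigger is an uncorrected QT, but the repeats are compared with the triggering 500 msec as a corrected QTc. The two agree only at 60 bpm. At slower rates the corrected value is smaller, so an ECG that confirms QT ≥500 can at the same time read below threshold on the scale that decides whether hourly ECGs begin.

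This matters for the next step. Escalation under (b) needs to know whether QT has stayed at or above 500 msec for more than 4 hours. With so few scheduled ECGs, the hourly repeats are what would show that. If they do not start, the rule does not itself generate the readings on which escalation depends. The cardiologist-consult sentence has the same gap, because it refers only to QTcF although one of the criteria above it is on QT.

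**Working it through.** There is no plan figure to reproduce. The check sets trigger and release side by side and converts between them.

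**Inputs.** The 500 msec QT trigger, the 450/470 msec and 30 msec QTcF conditions (Section 8.2.3), and the 450/470 msec baseline caps (Section 5.2.1, criterion 12). The heart rates are illustrative assumptions, because the documents give none.

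**Step 1: take the reading most favourable to the plan, QTc = QTcF.** Fridericia: QTcF = QT / (60/HR)^(1/3). Conversely, the QT at which QTcF reaches 500 is 500 × (60/HR)^(1/3).

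| Heart rate (bpm) | QTcF when QT = 500 | QT needed for QTcF = 500 |
|---|---|---|
| 45 | 454.3 | 550.3 |
| 50 | 470.5 | 531.3 |
| 55 | 485.7 | 514.7 |
| 60 | 500.0 | 500.0 |
| 70 | 526.4 | 475.0 |
| 80 | 550.3 | 454.3 |

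For example, at 50 bpm: 60/50 = 1.2, cube root 1.0627, and 500/1.0627 = 470.5.

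**Step 2: below 60 bpm.** At 50 bpm any QT from 500 up to about 531 msec fires (b) and can be confirmed on QT, yet its QTcF is below 500, so the condition for hourly repeats is not met. At 55 bpm the gap runs from 500 to about 515 msec, and at 45 bpm from 500 to about 550 msec.

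**Step 3: above 60 bpm.** At 80 bpm QTcF does not drop below 500 until QT is under about 454 msec, so repeats under (b) continue after QT has fallen below its own trigger.

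**Step 4: how often (a) covers the gap.** When (a) is also met, its own threshold can start the repeats. Assume the comparison baseline respects the criterion 12 caps, and take QT = 500.

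- 55 bpm, QTcF 485.7. Controls: baseline is at most 450, so the rise is at least 485.7 − 450 = 35.7 and (a) is always met. Impaired: (a) needs a baseline of at most 485.7 − 30 = 455.7, so baselines between about 456 and 470 are left uncovered.
- 50 bpm, QTcF 470.5. In either group (a) needs a baseline of at most 470.5 − 30 = 440.5.
- 45 bpm, QTcF 454.3. Impaired: not above 470, so (a) is never met. Controls: (a) needs a baseline of at most 454.3 − 30 = 424.3.
- Above 60 bpm, while QTcF is still 500 or more, the rise from the caps is at least 500 − 470 = 30 or 500 − 450 = 50, so (a) is met and repeats are due in any case.

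The practical loss is therefore confined to slow rates where (a) is not also met.

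**Step 5: limb (a).** If QTc means QTcF, trigger and release are identical and the error is zero.

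**The case against.** The best defence is that the sentence is shorthand. The two extra ECGs are there to confirm the original measurement, and asking whether a value remains above the threshold that triggered makes sense only on the same measure. For (a) that argument largely succeeds: QTc is most naturally read as QTcF. For (b) the same logic would make QTc mean uncorrected QT, which the words do not say, and no other section reconciles them.

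Section 8.2.3 also allows that, when a machine-read QTc is prolonged, "repeat measurements may not be necessary if a qualified medical provider's interpretation determines that the QTcF values are in the acceptable range". One could take this to mean that the corrected value should govern throughout. But it is a discretionary waiver for a prolonged QTc. It says nothing about a QT of 500 msec or more, and at 55 bpm the resulting QTcF of 486 is above both group limits.

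A third point is that little is lost. Other safeguards remain: continuous monitoring on QTcF and QT, Appendix 7's separate flag for QTcF above 480 msec, and investigator discretion to act sooner. That stands, and it limits the weight of the point.

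Two stronger readings are tempting but not supported.

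- A reader might infer that (a) fails as well, because a Bazett machine would read QTcF 475 at 55 bpm as 475 × (55/60)^(1/6) = 468, below 470. The documents name no machine correction, so this rests on an undocumented assumption.
- A reader might infer that absolute QT in (b) is a slip for QTcF, because (b) can fire with QTcF inside the group limits (QT 505 at 48 bpm is QTcF 469). But (b) is joined by an or, and firing on its own is what a backstop is for. The same wording appears in both paragraphs of the rule, which fits a deliberate choice equally well.

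**Conclusion.** The point holds for limb (b). Its trigger is uncorrected QT and its release is a corrected QTc, and the mismatch survives the most favourable reading of QTc. Followed literally, a confirmed QT of 500 msec at 55 or 50 bpm (QTcF 486 or 471) need not lead to the hourly ECGs on which escalation under (b) depends, unless (a) is also met. Above 60 bpm the effect is only that repeats run on past QT 500, where (a) would normally require them anyway. For limb (a) the wording is ambiguous and no error is shown.

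This is a minor correction to a safety instruction that sites must apply on the spot. The conversion assumes Fridericia for QTc, and the overlap with (a) assumes baselines within the criterion 12 caps. Without heart-rate data in the documents, no frequency can be claimed. The PK endpoints and their analysis are unaffected.

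**What to change.** In the start and stop sentence of Section 8.2.3, replace QTc values, in both places, with the measure that triggered the repeat: QTcF for (a), QT for (b). If both fired, require both to clear. Extend the 8-hour cardiologist-consult sentence so that it also refers to QT where (b) was the criterion.

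Keep (b) on absolute QT. Converting it to QTcF would also align the scales, but it would raise the QT needed at 50 bpm from 500 to 531 msec and so weaken the backstop in bradycardia. It would also add almost nothing to (a), because a postdose QTcF of 500 or more in an eligible participant already meets (a) (Step 4).

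The cost is a few words at the next amendment. QT and heart rate come from the machine and QTcF is already needed for (a), so no new data, staff or scheduled ECGs are required. The downside is a few more repeat ECGs at slow heart rates.
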